1.1 Primary Objective

To evaluate the efficacy of Amino Acid (15) Peritoneal Dialysis Solution in improving the nutritional status of patients receiving peritoneal dialysis.

1.2 Secondary Objectives

- Observe the effects of the solution on dialysis adequacy and peritoneal transport function.
- Monitor adverse events and complications to assess the short-term safety of the solution.

1.3 Exploratory Objective

To explore the mechanism by which Amino Acid (15) Peritoneal Dialysis Solution improves nutritional status in peritoneal dialysis patients through intra-abdominal amino acid supplementation.

2. Study Design

- **Study Type:** Interventional clinical study
- **Design:** Single-center, prospective, open-label, self-controlled (before-and-after comparison)

- **Total Study Duration:** 24 months (from study initiation to final report completion)
- **Intervention Period per Participant:** 6 months (starting on the enrollment day)
- **Sample Size:** 50 participants

3. Study Population

3.1 Inclusion Criteria

- Aged \geq 18 years.
- Receiving peritoneal dialysis for \geq 6 months.
- Serum albumin level $<$ 38 g/L.
- No history of peritonitis in the past 3 months and no hospitalization in the past 1 month.
- No severe heart, liver, or other organ dysfunction, or malignant tumors.
- Expected survival time $>$ 1 year.
- Good compliance and willingness to sign the informed consent form.
- Diagnosed with end-stage renal disease (ESRD) with estimated glomerular filtration rate (eGFR) $<$ 15 mL/ (min \cdot 1.73 m 2).

3.2 Exclusion Criteria

- Hypersensitivity or allergy to Amino Acid (15) Peritoneal Dialysis Solution or any of its components.
- Hepatic dysfunction (ALT/AST \geq 2 times the upper limit of normal).
- Taking medications that affect protein metabolism and unable to maintain a stable dose during the study.
- Need for adjustment of nutritional supplement doses during the study.
- Uncorrectable severe gastrointestinal reactions.
- Pregnant, lactating, or planning to undergo kidney transplantation.

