4.3 Concomitant Medications

- Participants must maintain stable doses of medications affecting protein metabolism and nutritional supplements throughout the study period.
- Any necessary dose adjustments due to severe clinical complications (e.g., severe infection) will result in participant withdrawal, with follow-up until symptoms stabilize.

5. Outcome Measures

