5.1 Primary Outcome Measure

Serum albumin (Alb) level: Measured at baseline (enrollment day), 3 months, and 6 months post-intervention.

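### Doses of supplements and protein-active medicines must be stable only from enrolment onward, so a change made just before the baseline albumin can be attributed to the solution.

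*Protocol*

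**What the plan says.** Three rules govern background treatment, and all are worded forward in time.

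- Section 3.2 excludes patients who are "Taking medications that affect protein metabolism and unable to maintain a stable dose during the study".
- Section 3.2 also excludes "Need for adjustment of nutritional supplement doses during the study".
- Section 4.3 states: "Participants must maintain stable doses of medications affecting protein metabolism and nutritional supplements throughout the study period".

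The design in section 2 is "Single-center, prospective, open-label, self-controlled (before-and-after comparison", and the intervention lasts "6 months (starting on the enrollment day". Section 5.1 has serum albumin "Measured at baseline (enrollment day), 3 months, and 6 months post-intervention". Enrolment, baseline and first use of the solution therefore share one day. Sections 6.1 and 6.2 describe no run-in and give no screening period of stated length.

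Section 3.1 does use look-backs for other conditions: "No history of peritonitis in the past 3 months and no hospitalization in the past 1 month", and a minimum of 6 months on peritoneal dialysis. Section 7.4 tests the primary outcome with a paired t-test or a Wilcoxon signed-rank test, without adjustment.

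**The concern.** In a before-and-after study the participant's own baseline is the only control. The comparison is clean only if background treatment that moves albumin has already had its effect by the time of the baseline sample. Sections 3.2 and 4.3 treat supplements and protein-active medicines as confounders, but guard against changes only after enrolment.

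Suppose a patient starts an oral supplement one week, enrols the next and keeps the same dose for 6 months. On these points the patient meets sections 3.1 and 3.2 and complies with 4.3. The baseline albumin precedes most of the supplement's effect and the 6-month value includes it. The paired test cannot separate that change from the solution's. The secondary nutritional measures in section 5.2, such as prealbumin, transferrin and SGA, are exposed in the same way. A repeat baseline sample taken at about the same time would help against regression to the mean but would not remove this problem.

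**Working it through.** **1. Does any rule give a look-back?**

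| Rule | Section | Period before baseline |
|---|---|---|
| Protein-active medicines, stable dose | 3.2, 4.3 | none |
| Nutritional supplements, no dose change | 3.2, 4.3 | none |
| Peritonitis | 3.1 | 3 months |
| Hospitalization | 3.1 | 1 month |
| Time on peritoneal dialysis | 3.1 | at least 6 months |

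The last three rows do not restrict supplements or medicines.

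**2. The plan's own figure.** Section 7.5 gives SD of change 4 g/L, difference 3 g/L, two-sided alpha 0.05 and power 80%. The normal approximation gives n = ((1.960 + 0.842) × 4/3)² = 13.95, rounded up to the stated 14. The SD and test are therefore understood as the plan uses them. This point does not dispute the sample size.

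**3. Inputs for the illustration.** From section 7.5: SD 4 g/L, 50 enrolled, 15% withdrawal, so 50 × 0.85 = 42.5, taken as 42 completers. Assumed, because the documents do not give them: a share f of participants (10%, 20%, 30%) carries a background rise of x g/L (1, 2, 3), and the solution has no effect.

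**4. Formulas.**
- Mean bias: b = f × x.
- SD of change when only some participants shift: s = √(16 + f(1 − f)x²).
- Noncentrality: b√n / s.
- Chance of a significant increase: upper tail of the noncentral t beyond the two-sided 5% critical value (2.010 at n=50, 2.020 at n=42). This treats the mixture of shifted and unshifted participants as approximately normal.

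Worked case, f = 30%, x = 3, n = 50: b = 0.9; s = √(16 + 0.21 × 9) = 4.230; noncentrality = 0.9 × 7.071/4.230 = 1.505; upper tail = 31.4%.

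**5. Results** (without bias: 2.5%).

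| Rise x (g/L) | Share f | Mean bias (g/L) | n=50 | n=42 |
|---|---|---|---|---|
| 1 | 10% | 0.1 | 3.7% | 3.6% |
| 1 | 20% | 0.2 | 5.3% | 5.0% |
| 1 | 30% | 0.3 | 7.5% | 6.8% |
| 2 | 10% | 0.2 | 5.3% | 5.0% |
| 2 | 20% | 0.4 | 10.0% | 9.0% |
| 2 | 30% | 0.6 | 17.2% | 15.1% |
| 3 | 10% | 0.3 | 7.3% | 6.7% |
| 3 | 20% | 0.6 | 16.8% | 14.7% |
| 3 | 30% | 0.9 | 31.4% | 27.0% |

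**6. Why a modest bias matters.** With SD 4, an observed mean rise of 2.010 × 4/√50 = 1.14 g/L is already significant at n=50 (1.25 g/L at n=42). Both lie well below the 3 g/L that section 7.5 calls clinically meaningful.

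**7. Direction.** A recently started catabolic medicine or a recently stopped supplement would lower later albumin. The same formula then applies with the sign reversed, and the bias works against the solution.

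**The case against.** **Prevalence is not documented.** The protocol does not say how many patients take supplements or when they began. Section 3.1 removes some occasions for a recent change (peritonitis, hospitalization, early months on dialysis), and section 3.2 removes anyone whose supplement dose still needs adjusting. This stands. A reader might infer that recent starts are a common route into the trial, because entry requires albumin below 38 g/L and low albumin is a plausible reason to start a supplement. The documents do not establish that.

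**Direction is not fixed.** A reader might also infer that the bias must favour the solution. Both rules cover every medicine that affects protein metabolism, and such medicines can act either way. Only recent starts or increases of nutritional support push toward the product.

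**The top of the range is generous.** A 3 g/L background rise equals the plan's whole clinically meaningful difference. At 1 g/L the false-positive chance is only 3.7% to 7.5% at n=50. Even the largest bias shown, 0.9 g/L, is under a third of 3 g/L. This also stands, and is why the full range is given.

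**The study period might include screening.** No screening length is stated, so this reading creates no look-back.

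**It could be left to an analysis plan.** Eligibility is fixed in the protocol. A later analysis could describe or set aside recent changers if dates were recorded, but could not restore a clean baseline for them.

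**Conclusion.** The gap is real. The stability rules begin at enrolment, enrolment is baseline, and a patient whose supplement or protein-active medicine changed just before is admitted. In this single-arm comparison the resulting albumin change is credited to, or held against, the solution.

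Under the stated assumptions the mean bias is 0.1 to 0.9 g/L toward the product, and the chance of a significant increase for an inert solution goes from 2.5% to about 4% to 31% at n=50 (about 4% to 27% at n=42). These figures rest on assumed shares and rises, and on the plan's SD of 4 g/L for the variation apart from the background rise. They do not show that the trial will be biased by that amount or in that direction. Confidence is high for the gap and medium for its size. The protocol should be changed, because the repair is cheap and a baseline cannot be retaken once treatment has started.

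**What to change.** Add to the inclusion criteria in section 3.1: any nutritional supplements and medicines affecting protein metabolism have been unchanged (not started, stopped or adjusted) for a pre-specified period before the baseline albumin; patients taking none throughout that period qualify.

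The sponsor should set and justify the length of the period. Section 3.1 already uses look-backs of 1 and 3 months, but for other purposes, so neither carries over automatically. The line belongs in 3.1: placed unchanged among the exclusions in 3.2, it would exclude the stable patients.

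Keep the forward-looking rules in 3.2 and 4.3. Record start, stop and change dates at screening, and allow patients who do not yet qualify to be re-screened.

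The cost is a short amendment and a medication-history check. Some patients would enter later, and some would not become eligible, which narrows recruitment at a single centre; section 6.1 allows 18 months for it. This change does not require a larger sample.

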3.3.2 Participant Exclusion

- Missing data > 10% of required outcome measures.
- Severe violation of the study protocol.

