7.2 Data Analysis Principles

- **Intention-to-Treat (ITT) Analysis:** All enrolled participants will be included in the ITT set, regardless of protocol adherence.
- **Per-Protocol (PP) Analysis:** Participants who complete the full intervention and have no major protocol violations will be included in the PP set for sensitivity analysis.

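### Section 4.3 can end follow-up before the month-6 albumin in participants with severe complications, and 3.3.2 can then exclude them, although 7.2 keeps everyone enrolled in the ITT set

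*Protocol*

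**What the plan says.** Five places in the protocol bear on what happens when a dose changes.

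- **3.2 Exclusion Criteria** lists "Need for adjustment of nutritional supplement doses during the study". The item before it reads "Taking medications that affect protein metabolism and unable to maintain a stable dose during the study".
- **4.3 Concomitant Medications** sets the on-study rule: "Participants must maintain stable doses of medications affecting protein metabolism and nutritional supplements throughout the study period". Its consequence is limited to one cause: "Any necessary dose adjustments due to severe clinical complications (e.g., severe infection) will result in participant withdrawal, with follow-up until symptoms stabilize". It does not say what follows a dose change made for any other reason.
- **3.3.1 and 3.3.2** list the withdrawal and exclusion reasons. Neither names a dose change. Section 3.3.2 does exclude participants with more than 10% of the required outcome measures missing, and also for "Severe violation of the study protocol". It does not say whether exclusion is from the study or from the analysis.
- **7.2 Data Analysis Principles** states "All enrolled participants will be included in the ITT set, regardless of protocol adherence". The per-protocol set is defined as "Participants who complete the full intervention and have no major protocol violations will be included in the PP set for sensitivity analysis".
- **7.6** handles missing data by multiple imputation. **6.2** provides a withdrawal visit for safety checks and for completing data.

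**The concern.** Section 4.3 does not separate leaving the study regimen from leaving data collection. A participant withdrawn under it is followed until the episode resolves, which may be well before month 6. Month-6 albumin is one of the two post-baseline values of the primary outcome, and no section requires it after withdrawal. Without it, the baseline-to-month-6 paired comparison has no observed value for that participant.

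The loss is unlikely to be random. The trigger is a severe complication, and the protocol's own example is a severe infection. Such participants are likely to be doing worse than the rest. The design is open-label with a single group compared with itself, so there is no control arm in which the same selection would cancel. If these participants drop out of the comparison, or are imputed as though they had followed the average course, the mean albumin change may look better than it was.

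**Working it through.** **1. The plan's own figure.** Section 7.5 gives SD of change 4 g/L, difference 3 g/L, two-tailed alpha 0.05 and power 80%. By the normal approximation, n = (4 × (1.960 + 0.842) / 3)² = 13.95, rounded up to 14, as stated. (An exact paired t calculation gives 16; this does not affect the point.) The check confirms that 4 g/L is the SD on which the plan rests, and it is used below.

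**2. Does a withdrawn participant cross the 10% limit in 3.3.2?** Section 5.2 lists 11 indicators at baseline and month 6 (7 nutritional, 2 adequacy, 2 transport), which makes 22 measurements. Section 5.1 adds 3 albumin values, giving 25. If only month 6 is missing, 11 + 1 = 12 are lost: 12/25 = 48%. Counting ultrafiltration every two weeks as about 13 further records (26 weeks / 2), and losing none of them, gives 12/38 = 32%. The protocol does not define how the 10% is counted, but on either count a participant without month-6 data exceeds it.

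**3. The sections side by side.** Section 4.3 can stop follow-up before month 6. The missing month-6 data then meet 3.3.2, which excludes the participant. Section 7.2 keeps the same participant in the ITT set. The protocol does not say which governs. The per-protocol set omits the participant in any case, because the full intervention was not completed.

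**4. What imputation has to work with.** If withdrawal comes before month 3 and follow-up ends, only the baseline albumin is available. If it comes later, the month-3 value is available too. Whether this captures a decline that starts with the complication cannot be judged from the protocol.

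**5. Illustration of size.** Suppose a fraction p with the worst course is left out altogether, and that course has correlation r with the albumin change. Then

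bias = SD × r × φ(z_p) / (1 − p).

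SD = 4 g/L is from 7.5; p and r are assumptions. With r = 0.5:

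- p = 0.10: φ(−1.282) = 0.1755; 4 × 0.5 × 0.1755 / 0.90 = +0.39 g/L.
- p = 0.15: φ(−1.036) = 0.2332; 4 × 0.5 × 0.2332 / 0.85 = +0.55 g/L.

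Simulated trials of 50 with no true change gave +0.38 g/L with 5 removed and +0.57 g/L with 8 removed (15% of 50 is 7.5). The nominal 5% test rejected in about 10% and 16% of them.

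Range over r, by the same formula:

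| r | p = 10% | p = 15% |
|---|---|---|
| −0.3 | −0.23 | −0.33 |
| 0 | 0 | 0 |
| 0.3 | +0.23 | +0.33 |
| 0.6 | +0.47 | +0.66 |
| 1 (upper limit) | +0.78 | +1.10 |

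All values are in g/L.

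**The case against.** A reader might infer something stronger from 3.2: that the criterion rests on an event that can occur only after enrolment, so that participants become ineligible in retrospect and the albumin change is biased upward. The protocol does not support this. The item speaks of a need, which can be foreseen at entry. It stands among other forward-looking entry judgements, such as inability to keep a stable medication dose and plans for a transplant. No section declares anyone ineligible afterwards. The 3.2 wording is ambiguous, but it is not itself a removal rule.

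Nor does 4.3 withdraw everyone whose supplement changes. It is limited to severe clinical complications, so a change made only because nutritional markers are falling is not its stated trigger.

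The most serious objection is that withdrawal is not deletion. Section 7.2 keeps all enrolled participants, 7.6 imputes missing values, 6.2 provides a withdrawal visit, and albumin is also measured at month 3. This stands against the figures above, which describe leaving participants out altogether. It does not settle the matter: 3.3.2 conflicts with 7.2 on who stays in, the withdrawal visit does not promise a month-6 albumin, and imputation helps only as far as the data it uses reflect the deterioration.

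The direction is also uncertain. If adjustments were unrelated to the albumin change there would be no bias, and if they fell mainly on improving participants the bias would be negative.

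**Conclusion.** The point holds as a conflict between sections, with a plausible route to outcome-related loss. Sections 4.3 and 3.3.2 can together remove participants whom 7.2 says are kept, and nothing secures their month-6 albumin. Section 3.2 leaves unclear when its supplement criterion is judged.

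Upward bias in the albumin change is plausible because the trigger is a severe complication and there is no control arm. It is most direct in the per-protocol set. In the ITT analysis it depends on whether imputation captures the deterioration.

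Size and direction cannot be computed from the protocol. The +0.4 to +0.6 g/L is an illustration. It assumes that 10-15% are left out entirely with correlation 0.5 to the change, neither of which the protocol gives; the 15% in 7.5 is withdrawal for all reasons. It amounts to roughly 13% to 19% of the 3 g/L difference (0.39/3 and 0.57/3). That would not by itself produce the planned effect, but it would matter for a 5% test of no change. The correction should be made, as it is cheap.

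**What to change.** 1. **3.2:** word the criterion as a change in nutritional supplement dose already planned or expected at screening.
2. **4.3:** state that a medication or supplement dose change after enrolment is recorded with its date, does not remove the participant from the ITT set, and does not stop collection of the scheduled 3- and 6-month albumin. This concerns data collection only and leaves the treatment of such patients as it is.
3. **3.3.2:** reconcile with 7.2, so that missing outcome data or a protocol violation cannot take an enrolled participant out of the ITT set. Say what exclusion refers to.
4. **Sensitivity analysis:** report one that handles albumin values after a dose change separately.

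**Cost:** protocol wording, and an already scheduled blood sample in the participants who would otherwise be lost. The drawback is that some ITT values will follow a supplement change and mix its effect with that of the study solution, which is why item 4 is needed. The per-protocol analysis does not solve this, because that set is itself selected.

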3.3 Withdrawal/Termination Criteria

3.3.1 Participant Withdrawal

- Failure to undergo dialysis as per protocol for 3 consecutive days.
- Two consecutive missed follow-up visits.

- Voluntary withdrawal by the participant.
- Intervention duration < 3 months.

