6.2 Specific Procedures

- Baseline Assessment (Enrollment Day):** Collect demographic data, perform physical examination, conduct laboratory tests (blood, urine, dialysate samples), evaluate peritoneal function, complete SGA scoring, and measure muscle mass.
- Intervention Period:** Conduct biweekly follow-up to record UF volume, AEs and assess medication compliance. Perform serum Alb testing and AE review at the 3-month follow-up.
- 6-Month Post-Intervention:** Repeat all baseline assessments to measure outcome indicators.
- Withdrawal Visit:** Complete safety assessments and data supplementation for participants who withdraw from the study.

7. Statistical Analysis Plan

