7.6 Missing Data Handling

Missing data will be addressed using multiple imputation methods to minimize bias in the analysis results.

8. Data Management & Quality Control

- **Data Collection:** Use Electronic Case Report Forms (eCRFs) combined with paper records; anonymize data using unique study IDs to protect participant privacy.
- **Data Verification:** Implement double data entry, with all modifications tracked and documented in the audit trail.
- **Equipment Calibration:** Calibrate testing instruments every 3 months to ensure measurement accuracy.
- **Personnel Training:** Provide uniform training on study protocols and Standard Operating Procedures (SOPs) to all study personnel before study initiation.
- **Metadata Removal:** Redact and remove metadata from all electronic documents before submission to ensure compliance with data privacy regulations.

9. Ethics & Compliance

- The study complies with the 2024 Declaration of Helsinki, Good Clinical Practice (GCP), and relevant national regulations.
- Approved by the Ethics Committee of Shanghai Tenth People's Hospital (Approval No.: SHSY-IEC-6.0/26K8/P01; Approval Date: January 9, 2026).
- Informed consent will be obtained from all participants (or legal representatives) before enrollment.
- All personally identifiable information (PII) and confidential commercial information will be redacted before any public disclosure.

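### Sections 3.3.1 and 6.2 plan no albumin after withdrawal for lapses in dialysis or attendance, so ITT month-6 values for these participants would be imputed rather than observed

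*Protocol*

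**What the plan says.** Protocol section 3.3.1 is a single list of withdrawal criteria. Beside voluntary withdrawal it places "Failure to undergo dialysis as per protocol for 3 consecutive days", "Two consecutive missed follow-up visits" and "Intervention duration < 3 months". It makes no distinction between stopping the study solution and leaving the study.

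Section 6.2 sets out what happens next: "Complete safety assessments and data supplementation for participants who withdraw from the study". Albumin is not named there. The only other follow-up after withdrawal is in section 4.3. It applies to withdrawals caused by dose adjustments for severe complications, and it lasts until the symptoms settle rather than to month 6.

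The primary outcome in section 5.1 is serum albumin, "Measured at baseline (enrollment day), 3 months, and 6 months post-intervention". On the analysis side, section 7.2 states: "All enrolled participants will be included in the ITT set, regardless of protocol adherence". Section 7.6 adds: "Missing data will be addressed using multiple imputation methods to minimize bias in the analysis results". Section 3.3.2 separately excludes participants with "Missing data > 10% of required outcome measures".

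**The concern.** An ITT analysis that disregards adherence needs outcomes from people who did not adhere. Here, lapses in dialysis or attendance are reasons for withdrawal, and no later albumin is planned once a participant is withdrawn. Followed as written, the protocol creates missing primary data, and creates it selectively.

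A participant who still uses the daily bag but misses two consecutive visits in month 2 would be withdrawn. Neither later albumin would then be scheduled, even if that person were willing to attend at months 3 and 6.

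Poorly adherent or intercurrently ill participants may plausibly gain less albumin than the rest, although the protocol does not show this. If they do, the estimated mean change leans towards those who did well. The design has no control arm in which similar losses could offset the effect. A later analysis plan can choose an imputation model, but it cannot recover blood that was never drawn.

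**Working it through.** **1. The sections side by side**

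| Section | Content | Consequence for month-6 albumin |
|---|---|---|
| 3.3.1 | Three days off protocol dialysis, or two missed visits in a row, is withdrawal | Participant leaves the schedule |
| 6.2 | One withdrawal visit, albumin not named | No month-6 value planned |
| 4.3 | Follow-up until symptoms settle, for one kind of withdrawal | Not tied to month 6 |
| 7.2 | All enrolled are in the ITT set | A value is needed for everyone |
| 7.6 | Multiple imputation, model not stated | The value is filled in |

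Baseline albumin is always kept, and the month-3 value is kept for anyone withdrawn after it. Only those withdrawn before month 3 have no scheduled albumin after baseline.

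**2. The plan's own sample size**

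Inputs from 7.5: SD of change 4 g/L, difference 3 g/L, two-sided alpha 0.05, power 80%.

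n = (4 × (1.960 + 0.842) / 3)² = 13.95, rounded up to 14. The stated figure reproduces under the normal approximation.

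Allowing for 15% withdrawal, 14 / 0.85 = 16.5, so 17. The 50 enrolled is a choice well above this. With 15% withdrawn, 50 × 0.85 = 42.5, so about 42 participants have an observed month-6 value. Paired-t power at n = 42 is 99.7%. The question is therefore bias, not power.

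**3. Possible size of the bias (illustration)**

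Assumptions: 15% withdrawn, completers gain 3 g/L, and the withdrawn would have changed by d. The protocol gives no value for d.

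All-enrolled mean = 0.85 × 3 + 0.15 × d. Overstatement by completers = 0.15 × (3 − d).

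| d (g/L) | All-enrolled mean (g/L) | Overstatement (g/L) | Share of 3 g/L |
|---|---|---|---|
| -2 | 2.25 | 0.75 | 25% |
| -1 | 2.40 | 0.60 | 20% |
| 0 | 2.55 | 0.45 | 15% |
| +1 | 2.70 | 0.30 | 10% |

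Imputation that does not model non-adherence would carry a similar bias in the mean.

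**4. Effect on the test if the true all-enrolled mean change is zero**

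Suppose completers do 1, 2 or 3 g/L better than the withdrawn (assumed). Their mean is then shifted by 0.15 × 1 = 0.15, 0.15 × 2 = 0.30 or 0.15 × 3 = 0.45 g/L. A completers-only paired t-test with n = 42 and SD 4 rejects in about 5.6%, 7.6% or 11% of trials instead of 5%.

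**5. How often the missed-visit rule could fire**

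Assumptions: the rule refers to the biweekly follow-up, misses are independent, and the per-visit miss rate is p. The protocol gives no miss rate. Let a(n) be the chance of no two consecutive misses in n visits, with a(0) = a(1) = 1. Then a(n) = (1 − p) × a(n−1) + p × (1 − p) × a(n−2), and the chance that the rule fires is 1 − a(n).

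| p | 13 visits (about 6 months) | First 6 visits (about 3 months) |
|---|---|---|
| 5% | 2.8% | 1.2% |
| 10% | 10.5% | 4.6% |
| 15% | 21.6% | 9.8% |

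The right-hand column is the window in which both later albumin values would go unscheduled. At p = 12% the 13-visit figure is 14.65%, close to the whole 15% allowance in 7.5, but that match depends on a chosen miss rate.

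**The case against.** The strongest reply is that the protocol is silent rather than prohibitive. The supplementation of data at the withdrawal visit is undefined and could include albumin, and nothing forbids a later draw. A reader might infer that the withdrawal visit takes no albumin, but the text supports only that albumin is not named. Even if it were taken, a value at withdrawal is not the month-6 value.

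It can also be said that 7.2 defines who is in the set and 7.6 fills the gaps, so the two are compatible. This stands in part. A reader might conclude that the analysis is ITT in name only, or that imputation must assume the withdrawn did as well as the rest. Neither follows, because 7.6 does not fix the model. It could condition on baseline and month-3 albumin and on recorded compliance, and that detail commonly sits in the analysis plan. What remains is that few or no non-adherers with an observed month-6 albumin would be available to inform any such model.

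The word for a missed visit is not fully settled either: 6.1 and 6.2 speak of biweekly follow-up and also of a follow-up at 3 months. The biweekly reading is the more natural one. If the rule meant only the outcome visits, it would cost almost nothing extra. Nor does 3.3.1 say whether dialysis during a hospital stay counts as per protocol, so a hospital stay cannot be cited as a sure trigger.

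Finally, the inclusion criteria in 3.1 ask for good compliance, so miss rates may be low.

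**Conclusion.** The point holds in limited form. Sections 3.3.1 and 6.2 end planned albumin collection because of lapses in dialysis or attendance, while 7.2 promises an analysis that disregards adherence. The affected month-6 values would be imputed rather than observed.

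On the stated assumptions (15% withdrawn, completers gaining 3 g/L, the withdrawn changing by -2 to +1 g/L), the mean change could be overstated by 0.30 to 0.75 g/L, or 10 to 25% of the 3 g/L difference in 7.5. The 15% and the 3 g/L come from the protocol, though 3 g/L is its target difference and not an expected result. The outcomes of the withdrawn and the miss rates are assumed. A reader might infer that the result is certainly biased upward. The documents do not show how withdrawn participants fare, so the most that can be said is that it could be.

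This should be fixed, because values not collected during the trial cannot be obtained later and the remedy is cheap. It does not by itself invalidate the trial.

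**What to change.** Leave the criteria for stopping treatment to the sponsor, and change only what is measured afterwards:

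- In 3.3.1, distinguish stopping the solution from leaving the study, and state that meeting the 3-day or missed-visit criterion does not by itself end outcome collection.
- In 6.2, name serum albumin among the measurements at the withdrawal visit.
- Keep the scheduled month-3 and month-6 albumin, and adverse event collection, for everyone who has not withdrawn consent.
- In 7.2 and 7.6, use these observed values in the ITT analysis and impute only what is still missing.
- Reconcile 3.3.1, 3.3.2, 6.2 and 7.2. In particular, say how the exclusion for more than 10% missing data fits with an ITT set of all enrolled participants.

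The cost is protocol wording and a few extra albumin draws. The ITT estimate will then include off-treatment values and may be slightly less favourable. The PP analysis already planned in 7.2 still shows the on-treatment effect.
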